#### 8. Other analyses with same data set

- Performance with number of cases since the beginning of the batch. [R1intendedOrder]
- Effects on performance of reader completing one session after another and with time of day [Calculate batch in day by assigning a clinic start time for each reader using date and time stamp for first case read for each ReportingSetID].

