#### 1.2 Existing knowledge

In the NHSBSP, each set of mammograms is read by two radiologists who each indicate if there should be a recall for further tests. Disagreements are referred for arbitration, usually by a third radiologist. Radiologists assess two mammograms per minute on average which equates to 120 in a 1-hour session. This is a highly skilled, pressurised but repetitive and frequently intellectually unchallenging activity. A vigilance decrement of performance decrease over time has been observed in similar repetitive visual tasks such as radar operator.

Data from an observational study using the Breast Screening Programme database for eight English breast screening centres for 3 years has shown that the probability of being recalled for further tests and of having cancer detected at screening is dependent on the time since the radiologist had a break from reading. For the first ten cases after a first reader break, the cancer detection rate for the whole process (including second reader and arbitration) is higher. These extra cancers detected are not associated with a higher probability of being DCIS rather than invasive, and have a similar mix of grades 1, 2 and 3 to the rest of the cancers detected at screening so this phenomenon is unlikely to be associated with increased overdiagnosis.

First and second readers read each batch of mammograms in the same order, thus their postbreak increases in cancer detection rate occur when reading the same women's mammograms.

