## 2 Trial Design

#### 2.1 Trial summary

The trial is a multi-centre cluster randomised parallel group superiority trial. The centres will be English Breast Screening centres with digital mammography equipment. The intervention is reversing the order in which the second radiologist reads each batch of mammograms. A cluster for randomisation is a batch of mammograms (circa 30 women's mammograms). The unit for analysis is the individual women's outcome.

The pre-pilot will be conducted in three screening centres for two weeks to ascertain the practical issues with implementation, and to test the Crystal report for data extraction. Concurrently a survey of all English breast screening centres will be conducted to ascertain key characteristics relevant to the trial which may differ between centres, such as the blinding of one reader to another's decision, and the method of arbitration used.

The trial will be implemented using an adaptation to the NBSS software used at participating centres.

The trial will last 16 months in 44 centres (1.5 million women). The first 12 months data (1.1 million women) will be collected from the NBSS database to determine whether the intervention affected cancer detection rate.

The full data set will be collected three years after the end of the study, to ascertain whether there was a decrease in rate of interval cancers (cancers presenting symptomatically in the three years after screening), and therefore whether the intervention reduced the number of cancers missed at screening.

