## 3.2 Secondary aims

To investigate the mechanism by which the intervention is hypothesised to increase cancer detection rate. This is made up of several parts:

- 1. What effect does the intervention have on recall rate?
- 2. How well does the arbitration process perform?
- 3. Does reversing the order in which the second reader reads the mammograms increase disagreement between readers
- 4. Does cancer detection rate and recall rate change with time since a break?

To determine whether reversing the order in which the second reader reads the mammograms affects missed cancer rate.

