## ii) Secondary

- 1. Recall rate in intervention and control groups
- 2. Referral rate to arbitration, recall rate and cancer detection rate from arbitration, and positive predictive value of arbitration by type of arbitration used. Sensitivity and specificity of arbitration using 3 years follow up data
- 3. Disagreement rate in intervention and control group
- 4. Change in disagreement rate, recall rate, cancer detection rate, and missed cancer rate with intended reading order (and cases since a cancer, recall, and mid-batch break)
- 5. Rate of cancers detected symptomatically in the three years subsequent to screening in intervention and control group. To be collected three years after the trial implementation is complete. This provides a measure of the difference in rates of cancer missed.

iii) Health economicsCost per extra cancer detectedCost per quality adjusted life year gained from the intervention

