#### Analysis 3:

This is exploratory follow-up analysis but will not form part of the analysis in the main paper

The third model will be used to determine whether there are particular circumstances in which the intervention is effective.

Predictors to be considered for inclusion will be added separately as fixed effects to the baseline model from analysis 2. Those predictors which improve the model (Wald statistic sig at 10% level) will be added to one model, with those with highest Wald statistic added first. Those for which the Wald statistic remains significant at the 10% level will be retained in the baseline model. Predictors to be considered for inclusion are number of readers involved in arbitration (categorical: 1/2/3 or more), arbitration policy (binary: all recalled cases arbitrated/disagreements only arbitrated), arbitration independence (same/ different readers read and arbitrate the case) whether reader 2 can see reader 1 opinion (categorical: yes on computer/yes but only on paperwork/no), how the mammograms from the previous screening round are displayed (categorical: digital/film pre-hung on a multi-viewer/film available in bag by the workstation), whether the batch was read immediately after another batch(categorical no/yes one reader/yes both readers), the number of cases in the batch, and where in the batch the case was intended to be read (number of cases from beginning/end).

The treatment will be added to this model. The interaction between treatment (intervention or control) and each of these predictors will then be considered for inclusion using the same process and criteria.

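### Aim 4 concerns time since a break, but SAP 8 measures only position in the batch, so a short post-break effect could be diluted by a factor of 1 to 4

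*Combined protocol and SAP*

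**What the plan says.** **The question.** Protocol 3.2, aim 4: "Does cancer detection rate and recall rate change with time since a break". The rationale uses the same exposure. Protocol 1.2 reports a higher detection rate over the ten cases that follow a first-reader break, and Protocol 1.4 uses the number of cases since a break as its proxy for time.

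**The protocol's measure.** Protocol 3.3, secondary outcome 4, looks at change "with intended reading order (and cases since a cancer, recall, and mid-batch break").

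**The SAP's measure.** The first item of SAP 8 is "Performance with number of cases since the beginning of the batch. [R1intendedOrder"]. The second is "Effects on performance of reader completing one session after another and with time of day", obtained by numbering each reader's batches within a day.

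**Batches and breaks.** SAP 6, Analysis 3, considers as a predictor "whether the batch was read immediately after another batch(categorical no/yes one reader/yes both readers"). The quality assurance list in SAP 3 records, as contamination, a reader who leaves a batch half-way and returns to it later. Protocol 1.2 gives a reading speed of two per minute, "which equates to 120 in a 1-hour session". Protocol 2.1 says "A cluster for randomisation is a batch of mammograms (circa 30 women's mammograms"), while Protocol 4 and SAP 2 use a batch of 40.

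**The concern.** Position in batch equals cases since a break only if every batch starts after a break and none is interrupted. The SAP provides for both exceptions. The first case of a batch read straight after another is coded as if the reader were fresh, and a case read just after a mid-batch pause is coded as if the reader had been reading for some time. The protocol's bracketed measure would have dealt with the second problem, but the SAP does not build it.

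At stake is the interpretation of aim 4. If the benefit of a break lasts only a few cases, counting every batch start as a break pulls the slope on position towards zero. The trial would then be less able to say whether the post-break effect that motivated it was present.

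**Working it through.** **1. Reproduce the plan's figure.** 2 per minute × 60 minutes = 120 cases in a one-hour session, as stated. Batches per session: 120/40 = 3 and 120/30 = 4. The number of batches read per break, *k*, is not stated. I take *k* = 1 to 4, where 3 to 4 requires a full session with no break between batches.

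**2. Short effect.** Assume a step *D* in the log odds over the first 10 cases after a break, and zero afterwards. Only one batch in *k* contains the step, so:

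- contrast of positions 1–10 with the rest = *D*/*k*;
- average within-batch slope = (slope in a batch that follows a break)/*k*.

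| Reading pattern | Share of *D* recovered | Dilution factor |
|---|---|---|
| Break before every batch | 1.00 | 1 |
| Break every two batches | 0.50 | 2 |
| 120 cases unbroken, batches of 40 | 0.33 | 3 |
| 120 cases unbroken, batches of 30 | 0.25 | 4 |

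Mid-batch breaks are not modelled here.

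**3. Other shapes, over an unbroken 120-case session.** Each effect was projected by least squares onto position in batch. For exponential decay, the first figure in each pair is for batches of 40 and the second for batches of 30.

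- Decay constant 10 cases: dilution 2.95 and 3.80.
- Decay constant 40 cases: 2.00 and 2.22.
- Decay constant 120 cases: 1.35 and 1.40.
- Linear decline: 1.0. Cases since a break = position + a constant for each batch, so the per-case slope is unchanged. Only 30/120 to 40/120 of the range is seen within any one batch.

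**4. What the reported slopes can exclude.** Supplement 3, section B, gives OR 0.99987 per case (95% CI 0.998 to 1.001) for reader 1 detection.

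- The least-squares slope of a unit first-ten step on positions 1 to *m* is (50 − 5*m*)/[*m*(*m*² − 1)/12]. For *m* = 30 this is −100/2247.5 = −0.0445. For *m* = 40 it is −150/5330 = −0.0281.
- The step matching the lower limit is exp[*k* × ln(0.998)/slope], with ln(0.998) = −0.0020.
- *k* = 1: OR 1.05 (*m* = 30) and 1.07 (*m* = 40).
- *k* = 4, *m* = 30: OR 1.20. *k* = 3, *m* = 40: OR 1.24.

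The limit is rounded. If it lies anywhere from 0.9975 to 0.9985, the ranges are 1.03 to 1.09 for *k* = 1 and 1.14 to 1.31 for *k* = 3 to 4. For scale, the trial's target of 8.3 against 7.8 per thousand is an OR of (0.0083/0.9917)/(0.0078/0.9922) = 1.065.

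**5. Recall.** The reported slope is 0.9971 per case (0.9966 to 0.9977, p<0.001). Over a batch this is 0.9971^29 = 0.919 to 0.9971^39 = 0.893, which is not flat.

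**The case against.** Intended order is a deliberate choice. Protocol 3.3 names it first for this outcome, and Protocol 5.4 explains that analysing by intended order limits the effect of readers departing from the sequence. Reading direction is allocated at random, whereas breaks are chosen by readers. Reversal also acts only within a batch, so the average gradient within batches is relevant in its own right. This stands, and it is why position in batch should be kept.

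The SAP also goes some way towards handling consecutive batches. It plans a subgroup of batches read first in the workday by both readers (SAP 3; SAP 6, Analysis 1), the Analysis 3 predictor, and the second item of SAP 8. These cover the gap only in part. The subgroup is for the treatment effect, and first of the day is not the same as first after a break. The Analysis 3 predictor is exploratory, must pass a 10% Wald criterion, and is interacted only with treatment. Numbering batches within a day counts a batch read after a long pause as late.

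A reader might infer that the effect is diluted three- to four-fold, that the flat slope says little about vigilance, or that this is the trial's only test of mechanism. The documents support none of these:

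- The 120-case figure converts a reading speed. It does not say that 120 cases are read without a break.
- A linear decline keeps its slope, and the recall slope is clearly negative, so the exposure is not insensitive.
- Aims 1 to 3 also concern mechanism.
- Supplement 3 describes change per case along the batch and does not claim that there is no vigilance decrement.

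**Conclusion.** The mismatch is real. Aim 4 and its rationale concern time or cases since a break, the SAP analyses position in batch, and no break-based exposure is built. A short post-break effect would be diluted by the number of batches read per break: 1 to 4, with 3 to 4 only for an unbroken session of 120 cases. Dilution is smaller for slower decay, and a linear decline is not diluted at all.

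The flat detection slope therefore counts against a steady within-batch decline but may miss a brief post-break gain. Depending on an unrecorded reading pattern, the gain at the edge of the reported interval is an OR of about 1.05 to 1.07, or about 1.20 to 1.24. These values assume a first-ten-cases step, equal batch sizes and a least-squares approximation. The primary outcome is unaffected. This is a worthwhile and inexpensive improvement to a secondary analysis.

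**What to change.** Keep intended position in batch as planned, and add to SAP 8 a pre-specified analysis:

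1. From the NBSS time stamps, define a break as a gap above a pre-set length between one reader's consecutive reads. Fix that length before the data are seen and vary it in a sensitivity analysis.
2. For each read, compute cases and minutes since the last break, running on across consecutive batches and restarting after a mid-batch break.
3. Use these as predictors of reader recall and cancer detection.
4. Report the position-in-batch slope separately for batches that do and do not follow a break, with the number of batches read per break.

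The cost is SAP wording and some programming. SAP 8 already uses date and time stamps, Table 3 in SAP 5 plans mean time per case, and SAP 3 identifies batches not completed in one session. The downside is that time since a break is partly chosen by readers, so the analysis is observational and sits beside the intended-order analysis rather than replacing it. Because Supplement 3 already reports the position slopes, the analysis should be labelled post hoc if it is added now.

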## **Supplement 3**

## A. Characteristics of Participating Centres

There are 80 breast screening centres in England, each centre represents a single or group of hospitals in a region. Of these, 46 centres agreed to take part, we were unable to contact the director of breast screening at 22 centres, six centres were interested but had equipment incompatible with the trial software, two did not want to take part as they already used the intervention for all cases, and four were simply not interested. The characteristics of centres taking part in comparison to other centres in England is detailed in table e1. One centre withdrew early from the trial due to practical difficulties experienced with the change to case order, data from their first four months is included in the analysis.

Table e1. Characteristics of centres taking part in comparison to those not taking part. Data for the year 2011-12

	Centres taking part (n=46)	Centres not taking part (n=34)	
Mean number of women screened	21,921 (10,355)	18,229 (10,349)	
in one year (sd)			
Mean percentage uptake ‡ (sd)	74.0 (3.3)	73.9 (5.6)	
Mean percentage recall (sd)	3.62 (1.24)	3.47 (1.23)	
Mean small (<15mm) cancer	3.2 (0.7)	3.4 (0.7)	
detection rate per thousand women			
screened who have previously			
attended screening (sd)			
Standardised detection rate incident	1.47 (0.21)	1.49 (0.22)	
round cancers (sd)			
Region:			
North East	1	3	
North West	10	1	
Yorkshire and the Humber	6	2	
East Midlands	2	6	
West Midlands	6	2	
East of England	5	6	
London	1	5	
South East Coast	5	1	
South Central	3	6	
South West	7	2	

<sup>‡The proportion of invited women who attend screening, expressed as a percentage

## **B.** Detailed Modelling Results

#### Multilevel analysis for cancer detection models

Measures of association

Table e2 shows results of multilevel models for case, batch and centre level factors associated with breast cancer detection rates in the UK. With all factors controlled for in the multilevel analysis, age of participants and having first ever screen were statistically significantly associated with the odds of breast cancer detection. Every one year increase in the age of participants increased the odds of cancer detection by 5% (OR 1.05; 95% CI 1.04 - 1.06, p<0.001). For participants who have never been screened before the odds of cancer detection were 73% greater than for those participants who have been screened before. When all the factors were controlled for in the final model, the odds of a participant being detected as having breast cancer if in the treatment arm was very similar to that in the control arm (OR 1.01; 95% CI 0.97 - 1.06, p=0.660).

## Measures of variation

Table e2 shows random-effect (measures of variation) results from the multilevel analysis. In Model 1 (the empty model), there was a significant variation in the log odds of cancer detection across the batches ( $\tau$  = 0.811, 95% CI 0.757 – 0.866) and across the centres ( $\tau$  = 0.058, 95% CI 0.012 – 0.104). According to the intracentre and intra-batch correlation coefficient implied by the estimated intercept component variance, 1.4% and 20.9% of the variance of cancer detection could be linked to the centre- and batch-level factors, respectively. Variations across batches and centres remained statistically significant, even after controlling for treatment and background factors in the final model 4, thereby giving credence to the use of multilevel modelling to account for batch and centre variations.

The median odds ratio (MOR) results also confirmed the evidence of batch and centre contextual phenomena modifying the likelihood of cancer detection. In Models 1 and 2 the batch level heterogeneity is high (MOR of 2.35), but the centre level heterogeneity is low (MOR of 1.26). When the model is adjusted for age and whether the woman has been screened before (Models 3 and 4) the batch level MOR (2.08) remains high and the centre level MOR (1.20) remains low.

Table e2: Factors associated with cancer detection rate identified by multilevel multivariable logistic regression models.

Variable	Model 1 a	Model 2 b	Model 3 c	Model 4 d			
	OR (CI)	OR (CI)	OR (CI)	OR (CI)			
FIXED-EFFECTS (measures of association)							
Treatment variable							
Treatment (vs. control)		1.01(0.96-1.06)		1.01(0.97-1.06)			
Background factors							
Age (per year of age)			1.052(1.048-1.055)	1.052(1.048-1.055)			
No previous attendance			1.73(1.62-1.86)	1.73(1.62-1.86)			
RANDOM-EFFECTS (measures	s of variation)						
Centre level							
Variance (SE)	0.058(0.012-0.104)	0.058(0.012-0.104)	0.038(0.011-0.065)	0.038(0.011-0.064)			
Intra-centre correlation (%)	1.40	1.39	0.96	0.96			
MOR	1.26	1.26	1.20	1.20			
Wald statistics (p-value)	0.014	0.014	0.006	0.006			
Batch level							
Variance (SE)	0.811 (0.757-0.866)	0.809(0.754-0.863)	0.598(0.546-0.650)	0.595(0.543-0.647)			
Intra-batch correlation (%)	20.90	20.85	16.19	16.13			
MOR	2.35	2.35	2.08	2.08			
Wald statistics (p-value)	<0.001	<0.001	<0.001	<0.001			

<sup>aModel 1 is the empty model, a baseline model without any predictor variable

Abbreviations: SE; standard error, CI; confidence interval, MOR; median odds ratio.

<sup>bModel 2 is adjusted for treatment variable

<sup>cModel 3 is adjusted for background factors (age and previous attendance)

<sup>dModel 4 is adjusted for treatment and background variables (age and previous attendance)

#### Multilevel analysis for recall rate models

#### Measures of association

Table e3 shows results of multilevel models for case, batch and centre level factors associated with recall rates in the UK. With all factors controlled for in the multilevel analysis, age of participants and having first ever screen were statistically significantly associated with the odds of recall. Every one year increase in the age of participants increased the odds of recall by 0.8% (OR 1.008; 95% CI 1.007 - 1.010, p<0.001). For participants who have never been screened before the odds of being recalled for re-evaluation were 189% greater than those for participants who have been screened before. When all the factors were controlled for in the final model, the odds of a participant being recalled for re-evaluation if in the treatment arm (OR 0.997; 95% CI 0.978 – 1.016, p=0.726) decreased by 0.3% compared to those in the control arm, though this association was not statistically significant.

#### Measures of variation

Table e3 shows random-effect (measures of variation) results from the multilevel analysis. In Model 1 (the empty model), there was a significant variation in the log odds of cancer detection recall across the batches ( $\tau$  = 0.104, 95% CI 0.092 – 0.116) and across the centres ( $\tau$  = 0.052, 95% CI 0.030 – 0.074). According to the intracentre and intra-batch correlation coefficient implied by the estimated intercept component variance, 1.5% and 4.5% of the variance of cancer detection recall could be linked to the centre- and batch-level factors, respectively. Variations across batches and centres remained statistically significant, even after controlling for treatment and background factors in the final model 4.

The MOR (1.36) in Model 1 across the batches suggests that batch heterogeneity is moderate. Controlling for treatment-level factor (Model 2) did not change the unexplained heterogeneity between batches. However, at the centre level the clustering effect is low (MOR of 1.24). The unexplained centre heterogeneity remained unchanged when all the factors were controlled for (Model 4). Thus, there were little variations between centres in the likelihood of recall.

Table e3: Factors associated with recall rate identified by multilevel multivariable logistic regression models.

Variable	Model 1 a	Model 2 b	Model 3 c	Model 4 d			
OR (CI) OR (CI) OR (CI)  FIXED-EFFECTS (measures of association)							
Treatment variable	•						
Treatment (vs. control)		0.993(0.974-1.013)		0.997(0.978-1.016)			
Background factors		0.000(0.07 : 2.020)		0.007 (0.070 2.020)			
_			1.008(1.007-1.010)	1.008(1.007-1.010)			
Age (per year of age)			1.008(1.007-1.010)	1.000(1.007-1.010)			
No previous attendance			2.89(2.82-2.97)	2.89(2.82-2.97)			
RANDOM-EFFECTS (measures	of variation)						
Centre level							
Variance (SE)	0.052(0.030-0.074)	0.052(0.030-0.074)	0.053(0.030-0.076)	0.053(0.030-0.076)			
Intra-centre correlation (%)	1.51	1.51	1.57	1.57			
MOR	1.24	1.24	1.24	1.24			
Wald statistics (p-value)	< 0.001	<0.001	<0.001	< 0.001			
Batch level							
Variance (SE)	0.104(0.092-0.116)	0.104(0.092-0.116)	0.033(0.023-0.044)	0.033(0.023-0.044)			
, .		. ,	. ,	,			
Intra-batch correlation (%)	4.54	4.54	2.55	2.55			
MOR	1.36	1.36	1.19	1.19			
Wald statistics (p-value)	<0.001	<0.001	<0.001	<0.001			

<sup>aModel 1 is the empty model, a baseline model without any predictor variable

Abbreviations: SE; standard error, CI; confidence interval. MOR; median odds ratio

<sup>bModel 2 is adjusted for treatment variable

<sup>cModel 3 is adjusted for background factors (age and previous attendance)

<sup>dModel 4 is adjusted for treatment and background variables (age and previous attendance)

